15.1 Screening Visit (Study Days -28 to -1) Procedures

Screening assessments must be performed within 1 to 28 days prior to the Week 0 Visit.

The following procedures will be performed at the Screening Visit:

- Informed consent.
- Inclusion/exclusion criteria.
- SLEDAI-2K and BILAG-2004.
- Medical and surgical history, including the first day of the last menstrual period for women of childbearing potential.
- Demographics.
- Complete physical examination.
- Height and Weight.
- Vital signs.
- 12-lead electrocardiogram (ECG).
- Clinical laboratory tests (chemistry, hematology, and urinalysis).
- Lipid panel.
- HbA1c.
- Serum pregnancy test.
- Hepatitis serology.
- IGRA test for TB.

- C3, C4 and anti-ds DNA antibodies.
- Serology (ANA, ENA; if history is unavailable)
- Contact the Interactive Phone/Web Response System (IXRS).
- Adverse events and concomitant medications.

Subjects will be allowed to repeat any screening procedure once, if necessary, if it is within the screening window.

15.2 Randomization Visit (Week 0) and First Dose Procedures

All evaluations will occur prior to the first dose of study drug, except as noted.

- Inclusion/exclusion criteria review.
- [REDACTED]
- [REDACTED]
- 28 Joint Count, SLEDAI-2K, BILAG-2004, PGA, and CLASI -Activity.
- Current medical condition review.
- Limited physical examination.
- Weight.
- Vital signs.
- Clinical laboratory tests.
- Lipid panel.
- Urine pregnancy test.
- C3, C4, and anti-ds DNA antibodies.
- [REDACTED]
- [REDACTED]
- [REDACTED]
- [REDACTED]
- Subject diary and study drug administration training.
- Contact IXRS and dispense study drug kits.

- Study drug administration under supervision of study staff and observation for at least 1 hour thereafter.
- Adverse events and concomitant medications.

15.3 Week 2 (\pm 3 days) and 6 (\pm 3 days) Procedures

- SLEDAI-2K.
- Current medical condition review.
- Limited physical examination.
- Weight.
- Vital signs.
- Clinical laboratory tests ■■■■■
■■■■■
- C3, C4, and anti-ds DNA antibodies.
- Hospital admissions.
- Subject diary review.
- Study drug accountability.
- Contact IXRS and dispense study drug kits.
- Adverse events and concomitant medications.

15.4 Week 4 (\pm 3 days) and 20 (\pm 5 days) Procedures

- 28 Joint Count, SLEDAI-2K, BILAG-2004, PGA, CLASI- Activity, and Safety of Estrogens in Lupus Erythematosus National Assessment (SELENA) Flare Index (SFI).
- Current medical condition review.
- Limited physical examination.
- Weight.
- Vital Signs.
- Clinical laboratory tests.
- C3, C4, and anti-ds DNA antibodies.
- Hospital admissions.
- Subject diary review.

- Study drug accountability.
- Contact IXRS and dispense study drug kits.
- Adverse events and concomitant medications.

15.5 Week 8 (\pm 3 days) and 16 (\pm 5 days) Procedures

- ■■■■
- ■■■■
- 28 Joint Count, SLEDAI-2K, BILAG-2004, PGA, CLASI-Activity, and SFI.
- Current medical condition review.
- Limited physical examination.
- Weight.
- Vital Signs.
- Clinical laboratory tests.
- Urine pregnancy test.
- C3, C4 and anti-DS DNA antibodies.
- ■■■■
- ■■■■
- Serum cortisol and aldosterone.
- Hospital admissions.
- Subject diary review.
- Study drug accountability.
- Contact IXRS and dispense study drug kits.
- Adverse events and concomitant medications.

15.6 Week 12 (\pm 5 days) Procedures

- 28 Joint Count, SLEDAI-2K, BILAG-2004, PGA, CLASI-Activity, and SFI.
- Current medical condition review.
- Limited physical examination.
- Weight.

- Vital Signs.
- Clinical laboratory tests.
- Lipid panel.
- C3, C4 and anti-DS DNA antibodies.
- HbA1c.
- [REDACTED]
- Hospital admissions.
- Subject diary review.
- Study drug accountability.
- Contact IXRS and dispense study drug kits.
- Adverse events and concomitant medications.

15.7 Week 24 (± 5 days)/Early Termination Procedures

- [REDACTED]
- [REDACTED]
- 28 Joint Count, SLEDAI-2K, BILAG-2004, PGA, CLASI-Activity, and SFI.
- Current medical condition review.
- Complete physical examination.
- Weight.
- Vital Signs.
- 12-lead ECG.
- Clinical laboratory tests.
- Lipid panel.
- Serum pregnancy test.
- HbA1c.
- [REDACTED]
- C3, C4 and anti-DS DNA antibodies.

■ [REDACTED]

■ [REDACTED]

- Hospital admissions.
- Subject diary review.
- Study drug accountability.
- Contact IXRS
- Adverse events and concomitant medications.

15.8 Follow-up Visit - Week 28 (\pm 5 days)

The following procedures will be completed at the follow-up visit 28 (\pm 5) days after the final dose of study drug:

- Current medical condition review.
- Limited physical examination.
- Weight.
- Vital signs.
- Clinical laboratory tests.
- Urine pregnancy test.
- Adverse events and concomitant medications.

16 INVESTIGATIONAL MEDICINAL PRODUCT (Study Drug)

16.1 Methods of Assigning Subjects to Treatment Groups

16.1.1 Randomization and Stratification

Subjects will be randomized according to computer-generated allocation scheme to receive either Acthar 1 mL (80 U) or placebo 1 mL administered every other day for 4 weeks followed by 2x/week for 20 weeks. The randomization will be stratified by location (US or outside the US) and prednisone equivalent dose (≤ 20 and > 20 mg/day). For each stratum, a separate randomization scheme will be produced. Both investigators and the subjects will be blinded to the treatment assignment. A block randomization will be performed. The biostatistician will decide on the details at the time of the creation of the randomization scheme.

16.1.2 IXRS

The investigator or designee will contact IXRS to register subjects at screening. The subject's identification (ID) number will be determined by the IXRS and will be used to identify the subjects for the duration of the study within all systems and documentation. Subject identification numbers will consist of 7 digits: the first 4 digits reflect the site number assigned to the Investigator and the last 3 digits are the subject number.

A subject ID number will not be assigned to more than 1 subject. If a subject is not eligible to receive treatment, or should a subject discontinue from the study, the subject ID number cannot be reassigned to another subject.

In the event that a subject is rescreened, they do not need a new subject ID number. At the Randomization Visit, qualified subjects who meet all of the eligibility criteria will be randomized into the study.

The investigator or designee must contact the IXRS to report a subject as a screen failure if the subject does not meet eligibility criteria prior to randomization.

The investigator or designee must contact IXRS to record each subject visit, to receive the study drug assignments, and to report any subject status changes.

The investigator must maintain a subject master log linking the subject ID to the subject's name. The investigator must follow all applicable privacy laws in order to protect a subject's privacy and confidentiality. Information that could identify a subject will be masked on material received by the sponsor.

16.2 Emergency Identification of Investigational Medicinal Product

In case of an emergency during the Randomized Treatment Period, when knowledge of the investigational product assignment is required for the medical management of an individual subject, the investigator may obtain the treatment assignment of the subject experiencing the emergency. The treatment blind for that subject may be broken by accessing the IXRS using instructions provided by the IXRS vendor. The investigator must notify the sponsor's MM or physician designee immediately after determining that it is necessary to unblind the treatment assignment. The investigator and sponsor should make every effort to document and limit the people who are unblinded to the subject's treatment assignment. The investigator must also indicate in source documents that the blind was broken and provide the date, time, and reason for breaking the blind.

16.3 Dosing Procedures

Both Acthar and the placebo are supplied as 5 mL multidose vials. Acthar vials contain 80 U of ACTH per mL. The vials should not be over pressurized prior to withdrawing the product. The vials should be warmed to room temperature before using and will be labeled according to all applicable national and local regulations.

The following treatments will be administered:

- Acthar 1 mL (80 U) SC doses every other day for 4 weeks, followed by 1 mL (80 U) SC 2x/week for an additional 20 weeks.
- Placebo (1 mL) SC doses every other day for 4 weeks, followed by 1 mL SC 2x/week for an additional 20 weeks.

The subject or subject's caregiver will administer the first dose of Acthar in the clinic under the supervision of study staff. The subject will remain in the clinic for at least 1 hour postdose to monitor for allergic or anaphylactic reactions. Thereafter, all doses will be administered by the subject or the subject's caregiver at home.

16.3.1 Treatment Discontinuation

Treatment with study drug should be discontinued if any of the following occur:

- Development of accelerated hypertension (defined as systolic blood pressure ≥ 180 and diastolic blood pressure ≥ 100 mm Hg) that cannot be managed by the adjustment of concomitant medications such as antihypertensive medications.
- Development of congestive heart failure (Class III or IV) that cannot be managed by the adjustment of concomitant medications such as diuretics and antihypertensive medications.
- Development of diabetic signs/symptoms (ie, HbA1c > 6.5 , or fasting plasma glucose > 126 mg/dL, or classic symptoms of hyperglycemia with random plasma glucose > 200 mg/dL) that cannot be managed by the adjustment of concomitant medications such as insulin and oral hypoglycemic agents.
- Development of any other adverse event (AE) of at least moderate intensity and possibly, probably or definitely related to study drug that cannot be managed by the adjustment of concomitant medications.

Missed doses of study drug should be discussed with the medical monitor.

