13.2 Exclusion Criteria

Subjects are ineligible for study participation if they meet any of the following criteria at the Screening Visit or the Randomization Visit.

1. Subject is from a vulnerable population, as defined by the US CFR Title 45, Part 46, Section 46.111(b) and other local and national regulations, including but not limited to, employees (temporary, part-time, full time, etc) or a family member of the research staff conducting the study, or of the sponsor, or of the clinical research organization, or of the IRB/IEC.
2. Subject is unwilling to receive, or is intolerant of, SC injections.
3. Subject has a history of sensitivity to ACTH preparations (including but not limited to Acthar and Synacthen).
4. Subject has a history of sensitivity to porcine protein products.
5. Subject has severe active lupus nephritis defined as serum creatinine > 2.5 mg/dL or protein creatinine ratio > 1.5 g/g, or subject has required hemodialysis within 3 months prior to the screening visit or is likely to require hemodialysis throughout the study.
6. Subject has active CNS manifestations of lupus (as evidenced by seizures, psychoses, organic brain syndrome, cerebrovascular accident, cerebritis, or CNS vasculitis) within the 3 months prior to the Screening Visit or develops CNS lupus between the Screening Visit and the first dose of study drug
7. Subject has Type 1 or Type 2 diabetes mellitus or is taking hypoglycemic medication (a history of gestational diabetes mellitus is not exclusionary). Subjects must not have glycosylated hemoglobin (HbA1c) > 6.5 at the Screening Visit.
8. Subject has received any steroid injection (intramuscular, intraarticular or intravenous [IV]) within 4 weeks prior to the Screening Visit (use of topical and/or inhaled steroids is not exclusionary).
9. Subject has received oral prednisone > 30 mg per day or equivalent, cyclosporine, or any nonbiologic investigational drug within 3 months prior to the Screening Visit.
10. Subject has received IV immunoglobulin (Ig) or plasmapheresis within 4 months prior to the Screening Visit.

11. Subject has received cyclophosphamide, abatacept, B cell targeted therapy (anti-CD-22 [epratuzumab] or belimumab), B cell depleting therapy (rituximab or other anti-CD20 agent, or anti-CD52 agent [alemtuzumab]), or any biologic investigational agent within 6 months prior to the Screening Visit.
12. Subject has any known contraindication(s) to Acthar ([Mallinckrodt, 2015](#)) including, but not limited to:

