 - Any known history of scleroderma, osteoporosis, or ocular herpes simplex. For the purposes of this study, osteoporosis is defined as evidence of vertebral or long bone fracture, or lumbar T-score > 2.0 SD below the mean of the reference population.
 - Any primary adrenocortical insufficiency, or adrenal cortical hyperfunction.
 - Any current congestive heart failure (defined as New York Heart Association Functional Class III to IV).
 - Peptic ulcer (within 24 weeks prior to the Screening Visit).
 - Recent major surgery (within 24 weeks prior to the Screening Visit).
13. Subject has a history of chronic active hepatitis including active or chronic hepatitis B, or acute or chronic hepatitis C. Subjects must have negative Hepatitis B surface antigen (HBsAg) or Hepatitis B core antibody (HBcAb) and negative Hepatitis C virus antibody (HCV) or HCV polymerase chain reaction (PCR) < 25 IU/mL (HCV PCR will be automatically analyzed if HCV is positive) at the Screening Visit.
14. Subject has a history of tuberculosis (TB) infection, any signs/symptoms of TB, or any close contact with an individual with an active TB infection. Subjects must not have a positive or indeterminate interferon gamma release assay (IGRA) for TB at the Screening Visit.
15. Subject has a clinically significant infection requiring administration of IV antibiotics or hospitalization in the 4 weeks prior to the Screening Visit or between the Screening Visit and the first dose of study drug.
16. Subject has known immune compromised status (not related to SLE or therapies for SLE), including but not limited to, individuals who have undergone organ transplantation or who are known to be positive for the human immunodeficiency virus.
17. Subject has any solid tumor malignancy currently diagnosed or undergoing therapy, or has received therapy for any solid tumor malignancy in the 5 years prior to the Screening Visit; with the exception of treated and cured basal cell carcinoma, treated and cured squamous cell carcinoma of the skin, and treated and cured carcinoma in situ of the cervix.

18. Subject has a diagnosis of, is undergoing therapy for, or has received therapy for a hematologic malignancy in the 5 years prior to the Screening Visit.

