22.2 Definitions

Adverse Event

An AE is any untoward or undesirable medical occurrence in a subject who is administered IMP, which does not necessarily have to have a causal relationship with this treatment.

Examples of AEs include but are not limited to:

- Clinically significant laboratory findings.
- Clinically significant changes in physical examination findings.
- An AE occurring due to IMP overdose whether accidental or intentional.
- An AE occurring from IMP abuse.
- An AE associated with IMP withdrawal.
- Unexpected Adverse Event.

An unexpected AE is defined as an AE, the nature and severity of which is not consistent with the applicable product information in the most recent version of the Investigator's Brochure.

SLE Activity Changes

All changes in SLE activity that are unequivocally due to progression of disease should not be reported as an AE unless they result in a SAE as defined below.

Serious Adverse Event

An SAE is defined as any untoward medical occurrence that at any dose results in any of the following outcomes:

- Death.
- A life-threatening AE.
- Inpatient hospitalization or prolongation of existing hospitalization.
- A persistent or significant incapacity or substantial disruption of the ability to conduct normal life functions.
- Results in a congenital anomaly/birth defect.

Important medical events that may not result in death, be life-threatening, or require hospitalization may be considered serious when, based upon appropriate medical judgment, may jeopardize the subject or subject and may require medical or surgical intervention to prevent one of the outcomes listed above. Examples of such medical events include allergic bronchospasm requiring intensive treatment in an emergency department or at home, blood dyscrasias or convulsions that do not result in inpatient hospitalization, or the development of drug dependency or drug abuse.

Death

Death is an outcome of an event. The event that resulted in death should be recorded and reported on the SAE Form. All causes of death must be reported as SAEs. The investigator should make every effort to obtain and send death certificates and autopsy reports to Mallinckrodt.

Life-Threatening Event

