23 SUBJECT DISCONTINUATION OR WITHDRAWAL

23.1 Subject Withdrawal

Subjects who discontinue, or are withdrawn from the study for any reason, will be considered early termination. All subjects who terminate early will be required to have the Early Termination safety assessments (see [Section 14.7](#)) to assess their continued well-being.

The reason for discontinuation will be recorded. A subject may be discontinued from the study for the following medical or administrative reasons:

Withdrawal by Subject

Subjects will be free to discontinue from the study at any time. Subjects who have received at least 1 dose of study drug but do not complete the study will not be replaced.

Adverse Event

If a dosed subject suffers an AE that, in the judgment of the investigator, sponsor or MM, presents an unacceptable consequence or risk to the subject, the subject will be discontinued from study drug. In addition, subjects who experience any of the adverse events described in [Section 15.3.1](#) will be discontinued.

Death

In the event that a subject dies during the study, death will be the reason for discontinuation.

Lost to Follow-up

Every effort should be used to maintain contact with subjects during their participation in the study. A subject may be considered lost to follow-up if there is no response to 3 attempts to reach the subject by telephone and no response to a certified letter sent to the last known address of the subject. Efforts to contact the subject should be noted in source documentation.

Met Withdrawal Criteria

If a subject develops a condition that meets any of the exclusion criteria ([Section 13.2](#)) or fails to meet an inclusion criteria ([Section 13.1](#)) during the study that is not considered to be an AE or is noncompliant (eg, has a positive pregnancy), the subject will be discontinued from study drug. Discontinuation from study drug is also mandated for safety and/or tolerability issues as outlined in [Section 15.3.1](#)).

Worsening of Disease Activity

Subjects may be withdrawn if, in the opinion of the investigator, there is a lack of efficacy during the study.

Other

If the above reasons are not applicable, please use the “Other” option and provide the appropriate reason for subject withdrawal.

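### Section 16.3.1 requires study drug to stop for new Class III–IV heart failure only when it cannot be managed, although 13.2 lists that condition as a contraindication to Acthar and 23.1 does not clearly close the gap

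*Combined protocol and SAP*

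**What the plan says.** **At entry.** Criterion 12 of section 13.2 excludes a subject where "Subject has any known contraindication(s) to Acthar" applies. One listed item is "Any current congestive heart failure (defined as New York Heart Association Functional Class III to IV"). Nothing in that item exempts heart failure that is under control with medication.

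**On treatment.** Section 16.3.1 lists the events for which study drug should be discontinued. The second is "Development of congestive heart failure (Class III or IV) that cannot be managed by the adjustment of concomitant medications", with diuretics and antihypertensives given as examples. The only sentence there about interrupted dosing is "Missed doses of study drug should be discussed with the medical monitor".

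**Withdrawal.** Section 23.1 offers three routes:
- The Adverse Event paragraph stops study drug when the investigator, sponsor or medical monitor judges the risk unacceptable.
- The same paragraph makes discontinuation mandatory for the listed treatment-discontinuation events. It cites 15.3.1, evidently meaning 16.3.1.
- The Met Withdrawal Criteria paragraph begins "If a subject develops a condition that meets any of the exclusion criteria", adds failure of an inclusion criterion as an alternative, and continues "during the study that is not considered to be an AE or is noncompliant". The consequence is mandatory discontinuation of study drug.

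**Adverse events.** Section 22.2 states that "An AE is any untoward or undesirable medical occurrence in a subject who is administered IMP", whether or not it is caused by the treatment.

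**Dosing setting.** After the supervised first dose, section 16.3 says "Thereafter, all doses will be administered by the subject or" a caregiver, at home.

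**The concern.** The protocol treats Class III–IV heart failure as a reason not to give Acthar. When the same condition arises during treatment, it requires a stop only if adjusting other medicines fails. A subject with new Class III failure who has started a diuretic could therefore go on injecting at home without any departure from 16.3.1.

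The event is foreseeable: section 10.5 names fluid retention and raised blood pressure among the common reactions to Acthar. What is at stake is the safety of a subject who develops heart failure, and whether two sites would act alike when it happens.

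**Working it through.** No figure in the plan depends on this rule, so the check is mainly a comparison of text.

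**Step 1: same condition, different rule.** Section 13.2 criterion 12 and the second bullet of 16.3.1 both refer to Class III to IV congestive heart failure. The first has no qualifier; the second applies only when management fails. Section 16.3.1 also names accelerated hypertension and diabetic signs or symptoms. Of these three named conditions, heart failure is the only one that also appears among the contraindications spelled out in criterion 12. That list is stated not to be exhaustive.

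**Step 2: what counts as managed.** Section 16.3.1 gives no target class, time limit or assessor. If *managed* means return to Class I–II, the subject no longer has the condition that criterion 12 describes, and the conflict ends once that point is reached. If it means symptoms are tolerable on diuretics while the subject remains in Class III, dosing continues through a listed contraindication. The text allows either meaning.

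**Step 3: dosing meanwhile.** Sections 16.3, 16.3.1 and 23.1 contain no rule to hold doses while treatment is tried. To show what a visit interval represents, using Table 8-1 and the twice-weekly regimen:
- Nominal interval after Week 8: 4 weeks × 2 doses = 8 doses; 8 × 80 U = 640 U in the Acthar arm.
- This is not a maximum. With the Week 12 visit 5 days early and the Week 16 visit 5 days late, the interval is 28 + 5 + 5 = 38 days, and 38/7 × 2 = 10.9, so about 10 to 11 doses.

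**Step 4: does 23.1 settle it?** This depends on what the adverse-event phrase in the Met Withdrawal Criteria sentence limits.
- *It limits the exclusion-criteria clause.* New heart failure in a dosed subject is an adverse event under 22.2, so the sentence does not reach it. The sentence grants no discretion; it simply does not apply. What remains is 16.3.1 and the separate judgment-based stop in the Adverse Event paragraph. A stop is permitted but not required.
- *It limits only the inclusion-criteria clause.* New Class III–IV heart failure meets an exclusion criterion, so study drug must stop, managed or not. The qualifier in 16.3.1 then has no effect.

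One indication favours the first reading. Criterion 7 excludes anyone taking hypoglycemic medication, yet 16.3.1 lets new hyperglycemia be managed with insulin or oral agents. On the second reading, starting insulin would itself force a stop, and that allowance would also be empty. This does not settle the matter.

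**Step 5: other safeguards.** A hospital admission for heart failure would make the event serious and reportable within 24 hours (22.2, 22.4). All adverse events are followed up (22.4), and the medical monitor reviews safety data (27.2). Heart failure is not among the adverse events of special interest in 22.5. None of these is an automatic stop or hold.

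**The case against.** The strongest reply is that this is deliberate. Entry rules and on-treatment rules often differ, and 13.2 applies at screening and randomization. All the events in 16.3.1 carry the same manage-first condition, including blood pressure and glucose, which are also restricted at entry. Any one of the investigator, sponsor or medical monitor can trigger a stop on judgment, and many investigators would stop at once. Section 22.1 also sends sites to the Prescribing Information and the Investigator's Brochure, which are not available here.

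Most of this stands, and it limits the weight of the point. It does not explain why dosing may continue through a condition that the protocol itself calls a contraindication to the drug, and 16.3.1 gives no reason. The judgment-based stop permits the right action without requiring it.

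A reader might go further and infer that 16.3.1 and 23.1 contradict each other. The documents do not support that. Section 16.3.1 lists events that are sufficient for stopping; it does not say that study drug must continue otherwise. Section 23.1 adds its stops cumulatively. A site facing the stricter reading of 23.1 satisfies both sections by stopping, so on that reading the flaw is redundancy and the safety gap is closed.

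It is also fair to say that a site-level rule acts only once heart failure is recognized. It does not protect against undetected onset between visits.

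**Conclusion.** The point holds as an inexpensive safety improvement of minor to moderate weight. Section 16.3.1 as written permits continued dosing in a state that criterion 12 lists as a contraindication, with *managed* undefined and no hold. The gap is real if the adverse-event phrase in 23.1 limits the exclusion-criteria clause; otherwise only redundant wording needs tidying. The conclusion rests on the protocol's own classification in 13.2, not on outside labeling.

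Two stronger inferences should be avoided. One is a count of subjects likely to be affected: the documents give no incidence of heart failure in this population, so any count would be an assumption. The other is to treat 640 U as a ceiling on exposure between visits: it is the nominal four-week dose in the later part of the schedule. No effect on efficacy, bias or power is claimed.

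**What to change.** 1. **Section 16.3.1, second bullet.** Make it unconditional by ending it after the class and naming NYHA Class III or IV. If the sponsor wants an exception, define successful management as return to Class I–II, hold dosing until then, and require medical monitor agreement before restarting.
2. **Section 23.1, Met Withdrawal Criteria.** Reword the sentence so that recording a criterion-12 contraindication as an adverse event does not remove the mandatory stop.
3. **Editorial only.** Correct the two references in 23.1 from 15.3.1 to 16.3.1.

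**Cost.** An amendment to the wording and a letter to sites. No visits or tests are added: section 19.4 already has lungs, heart and extremities examined at every visit.

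**Downside.** There may be a few more discontinuations in either arm, since the rule is applied blind. Under 21.6, a subject whose Week 16 data are then missing counts as a nonresponder. With the 80 mITT subjects per group assumed in 21.11, each such subject who would otherwise have responded lowers that arm's response rate by 1/80 = 1.25 percentage points. Collecting the Week 16 assessments after study drug is stopped would avoid that loss.
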